## 4.2 Study Population

# 4.2.1 Approximate Number of Subjects

Approximately 30 patients will participate in the EC-LBBAP study to be conducted at Geisinger Heart Institute.

IRB NUMBER: 2022-0917
IRB Approved: 04/18/2024

All patients will share the same recruitment process, inclusion and exclusion criteria and same surgical procedure. Twenty patients will undergo intraprocedural transthoracic echocardiogram via standard practices. An additional 10 patients will undergo intraprocedural transthoracic echocardiogram using a hand-held ultrasound device.

#### 4.2.2 Inclusion Criteria

The following is the inclusion criteria for the EC-LBBAP study:

- 1. Patients > 18 years of age
- 2. Patient with an indication for permanent pacemaker or ICD utilizing conduction system pacing lead for bradycardia or cardiac resynchronization therapy
- 3. Patient is willing to comply with all study procedures and be available for the duration of the study.

#### 4.2.3 Exclusion Criteria

The following patients or situations are excluded in the EC-LBBAP study:

- 1. Inability to provide informed consent
- 2. Pregnant
- 3. Enrolled in a concurrent study that may confound the results of this study.

#### 4.3 Recruitment

Potential participants will be identified by clinician referrals. Research staff will contact potential subjects and invite them to participate.

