#### 4 STUDY DESIGN

## 4.1 Description

The EC-LBBAP study is a prospective, single-center, observational research study. The study team will identify all patients who satisfy the inclusion and exclusion criteria. The study team will evaluate the feasibility and success rates of echocardiogram guided LBBAP lead implantation.

Eligible patients would undergo LBBAP using Medtronic 3830 lead and C315His sheath. LBBAP will be confirmed at implant using left bundle potentials recorded from the lead, ECG morphology during unipolar and bipolar pacing, peak LV activation time and lead depth in the 2D transthoracic echo at implant.

During implant procedure, transthoracic echo windows will be identified and documented: Parasternal short and long axis, apical 2 and 4 chamber views and subcostal views to visualize the proximal interventricular septum. Following venous access using cephalic vein cut-down or ultrasound guided axillary vein access, the lead implantation in the left bundle branch region will be guided by echocardiography.

Retrospectively, the study team will identify 30 consecutive previous patients who satisfy inclusion and exclusion criteria (control patients). The study team will compare the difference in procedural success between Case and Control patients.

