#### Visit 1 – Baseline

The following activities will be completed at Visit 1 (Baseline):

• Subjects will be screened to ensure they meet ALL the inclusion criteria and NONE of the exclusion criteria.

IRB NUMBER: 2022-0917 IRB Approved: 04/18/2023

- Subjects will sign an Informed Consent form before any of the study related procedures are performed.
- Demographic
- Medical history
- Concomitant medication specifically ACE/ARB, beta blockers, diuretics, and antiarrhythmics use
- Relevant co-morbidities will be recorded
- NYHA Functional Classification
- Collection of device characteristics and implanted system description.
- EC-LBBAP research procedure \*

Intraprocedural transthoracic echocardiogram\*

Fluoroscopy duration for LBBAP lead implantation

Procedural duration for LBBAP lead implantation

Total fluoroscopy duration

Total procedural duration

Success of LBBAP

- 12-lead ECG (Rhythm Strips)
- Adverse Events related to echocardiogram

\*The use of the EC-LBBAP may add approximately 15 minutes of time for total procedure but may lower the fluoroscopy and procedure duration for LBBAP lead implantation. Additionally, this may improve the safety and success of the procedure.

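### Cases come by clinician referral and consent, controls as a consecutive retrospective series, so selection of unknown size and direction may be mixed into the Case-Control comparison of procedural success

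*Combined protocol and SAP*

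**What the plan says.** **Cases.** Section 4.3 (Recruitment) states "Potential participants will be identified by clinician referrals" and continues "Research staff will contact potential subjects and invite them to participate". Under Visit 1 – Baseline, "Subjects will sign an Informed Consent form before any of the study related procedures are performed". Section 4.1 (Description) describes the scope more broadly: "The study team will identify all patients who satisfy the inclusion and exclusion criteria".

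**Controls.** Section 4.1: "Retrospectively, the study team will identify 30 consecutive previous patients who satisfy inclusion and exclusion criteria (control patients"). Section 4.9.1 gives manual chart review as the means of obtaining data.

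**Shared criteria.** The criteria applied to both groups include inclusion 3, "Patient is willing to comply with all study procedures and be available for the duration of the study", and exclusion 1, "Inability to provide informed consent". No rule says how either is to be applied to a past patient.

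**Comparison.** Section 4.1: "The study team will compare the difference in procedural success between Case and Control patients". Section 4.8 lists two-group tests (chi-square or Fisher, t or rank tests) with no matching or adjustment. It adds that test results are not conclusive and will serve the design of a larger prospective study.

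Section 4.2.1 says that all patients share one recruitment process. That sentence concerns the 30 enrolled patients (20 with standard echo, 10 with a hand-held device), and retrospective controls are not recruited at all.

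**The concern.** A consecutive series takes patients as they come. Referral followed by consent passes them through two decisions, the clinician's and the patient's. If either decision is related to how hard the implant is, the groups differ before echo is used.

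The protocol's own text makes this plausible in both directions. Section 2 says LBBAP is hard when the sheath cannot be set perpendicular to the septum and that echo may help in most such situations, which is a reason to refer difficult patients. Section 4.1 relies on transthoracic views of the proximal septum, which is a reason to refer patients who image well. The baseline list in section 4.5 has no measure of septal or sheath difficulty, so an imbalance of this kind could not readily be seen or corrected afterwards.

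There is a second, smaller gap on the control side. Two of the criteria depend on a study that past patients were never offered. Without a rule, one reviewer might ignore them and another might infer availability from completed follow-up, which would select controls on events after the implant.

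At stake is the estimated gain in success that is handed to the larger study.

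**Working it through.** **1. Entry routes side by side**

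| | Cases | Controls |
|---|---|---|
| Found by | clinician referral (4.3) | retrospective identification (4.1) |
| Consecutive | not stated | yes |
| Invitation and consent | yes (4.3, Visit 1) | none described |
| Log of eligible patients not entered | none planned | none planned |

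**2. Which criteria can be read from a chart**

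| Criterion | Past patient |
|---|---|
| Inclusion 1, age | yes |
| Inclusion 2, device indication | yes |
| Inclusion 3, willing and available | no |
| Exclusion 1, unable to consent | only poorly |
| Exclusion 2, pregnancy | yes |
| Exclusion 3, concurrent study | usually |

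Four of the six can usually be applied alike to both groups. Two cannot.

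**3. What the comparison estimates**

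Expected observed difference = echo effect + selection difference.

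The second term does not shrink with more patients, and the unadjusted tests do not separate the two.

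**4. Illustration of size**

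Inputs from the documents: 30 cases (4.2.1), 30 controls (4.1), and usual LBBAP success of 80-90% (section 2). The documents give no alpha, power or expected difference, so there is no plan figure to reproduce. Assumptions: true echo effect zero, two-sided alpha 0.05, and the selection gaps shown.

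Method: for every pair of success counts (x cases, y controls), the probability is Bin(x; 30, p1) × Bin(y; 30, p2). These are summed over the pairs where the test rejects, and over the pairs with x > y.

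| Success, cases vs controls | Fisher rejects | Chi-square (uncorrected) rejects | Cases numerically better |
|---|---|---|---|
| equal, 80-90% | 0.9-2.2% | 4.9-5.4% | 41-44% |
| 90% vs 85% | 3.0% | 9.5% | 65% |
| 90% vs 80% | 9.6% | 19.4% | 82% |
| 80% vs 90% | 9.6% | 19.4% | 10% (controls better 82%) |

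In expected counts, 90% vs 80% is 30 × 0.90 = 27 against 30 × 0.80 = 24, or three patients. The standard error of that difference is √((0.90 × 0.10 + 0.80 × 0.20)/30) = √(0.25/30) = 0.091. A 10-point selection gap is thus about 1.1 standard errors: seldom significant, but enough to set the sign of the estimate in most studies.

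**5. Consequence for the larger study**

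Assume control success of 80%, a true echo gain of 5 points and a selection gain of another 5, so that 90% vs 80% is expected. At 80% power and two-sided 5%, the number per group is

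n = [1.960√(2p̄(1−p̄)) + 0.842√(p1(1−p1) + p2(1−p2))]² / (p1−p2)², where p̄ = (p1+p2)/2.

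- Sized on 90% vs 80%: p̄ = 0.85, n = 199 per group.
- Needed for the true 85% vs 80%: p̄ = 0.825, n = 906 per group.

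If selection ran 5 points the other way, the expected observed difference would be 5 − 5 = 0 and a real gain would be hidden.

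**The case against.** **Stakes.** The study is declared observational and exploratory, and section 4.8 disclaims conclusions. The first primary endpoint in section 4.6 is a success rate with echo, not a contrast. The Case-Control comparison of success appears only in section 4.1. The primary duration endpoint names historic data from prior studies at the site, which may be another comparator. All of this is correct and lowers the weight of the point. It does not dispose of it, because section 4.8 also sends these results into the design of a larger study.

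**Contradiction between 4.1 and 4.3.** A reader might infer that the two sections conflict. They can be read together, with referral as the channel and all eligible patients as the scope. The text does not say that referral is the only route, that clinicians choose by difficulty or image quality, or even that the referral is to the study rather than for a device. What stands is that nothing ensures every eligible patient is referred, and no log would show it.

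**A false benefit.** A reader might also infer that the design will manufacture an echo effect. The documents do not support that: the bias could favour cases, work against them, or be negligible.

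**Criteria.** It is tempting to say that controls are screened on criteria a chart cannot show. That is true of inclusion 3 and partly of exclusion 1. It is not true of the other four. Nothing says that reviewers would use completed follow-up as a proxy, and since LBBAP is confirmed at implant, any link from later availability to success would be indirect.

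**Remedy.** Waiving exclusion 1 for controls alone would create a new imbalance, and consecutive approach does not remove refusal of consent. Both objections stand, and the fix below allows for them.

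**Conclusion.** The concern holds in a limited form. Cases and controls enter by different routes, so the groups may differ by selection, in either direction and by an unknown amount. The unadjusted comparison of procedural success could mix that difference with any effect of echo guidance. The non-conclusive label reduces the consequence but does not stop a biased estimate from reaching the larger study.

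The different routes and the absence of a log, matching or adjustment come from the documents. The selection gaps of 5 and 10 points, the zero or 5-point echo effect, the two-sided 5% level and the 80% power are assumptions. Under them, a 10-point gap fixes the apparent direction in 82% of studies and raises chi-square rejection from about 5% to 19.4%. These figures show how sensitive a 30 vs 30 comparison is. They do not predict this study's bias. The point is a worthwhile, inexpensive improvement and does not invalidate the study.

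**What to change.** **Section 4.3.** Have research staff screen the implant schedule and approach consecutive patients planned for LBBAP, in line with the scope stated in 4.1. Keep a log of those not enrolled, with reasons.

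**Section 4.1.** Select controls consecutively on criteria verifiable in the chart as of the implant date (age, indication, pregnancy, concurrent study), without reference to outcome or completed follow-up. State that inclusion 3 is not assessable in controls. Apply exclusion 1 where the chart documents incapacity at implant, so that it is not waived for controls only.

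**Reporting.** Give the log counts with the results, and state that refusal of consent among cases remains as a difference the design cannot remove.

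**Cost.** Protocol wording, more patients to approach, some loss of the convenience of referral, and a short log kept by existing staff. No extra patients or procedures.

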## 4.4 Study Duration

### 4.4.1 Approximate Duration of Subject Participation

Subjects will participate in the study for approximately 3 months (+/- 1 week). This includes a monitoring (follow up) period which starts immediately after signing the Informed Consent and completing the baseline visit (visit 1).

IRB NUMBER: 2022-0917 IRB Approved: 04/18/2024

## 4.4.2 Approximate Duration of Study

This study will be completed in approximately 18 to 24 months duration. The end of the EC-LBBAP study is the completion of data entry and statistical analysis.

This study duration approximation is composed of the following stages:

- Screening and Enrollment Stage enrollment of 30 patients from Geisinger Heart Institute is expected to take 15-18 months based on enrollment rate of 1 to 3 subjects per month.
- Monitoring Stage based on the planned 3 month monitoring period for each patient, last patient completed is expected 10-12 months from the study beginning.
- Data Collection Stage data entry and management are ongoing leveraging the electronic data capture system and secured database.
- Statistical Processing and Data Analysis is expected to take 1-3 months from the data entry of the last patient visit or the last patient enrolled.

#### 4.5 Procedures

The EC-LBBAP study methodology is composed of:

- 1 scheduled clinic visits (baseline)
- 2-week follow-up monitoring period for device evaluation and adverse events (device clinic visit).
- 3-Month follow-up/exit visit for device evaluation and adverse events (device clinic visit).

#### Visit 1 – Baseline

The following activities will be completed at Visit 1 (Baseline):

• Subjects will be screened to ensure they meet ALL the inclusion criteria and NONE of the exclusion criteria.

IRB NUMBER: 2022-0917 IRB Approved: 04/18/2023

- Subjects will sign an Informed Consent form before any of the study related procedures are performed.
- Demographic
- Medical history
- Concomitant medication specifically ACE/ARB, beta blockers, diuretics, and antiarrhythmics use
- Relevant co-morbidities will be recorded
- NYHA Functional Classification
- Collection of device characteristics and implanted system description.
- EC-LBBAP research procedure \*

Intraprocedural transthoracic echocardiogram\*

Fluoroscopy duration for LBBAP lead implantation

Procedural duration for LBBAP lead implantation

Total fluoroscopy duration

Total procedural duration

Success of LBBAP

- 12-lead ECG (Rhythm Strips)
- Adverse Events related to echocardiogram

\*The use of the EC-LBBAP may add approximately 15 minutes of time for total procedure but may lower the fluoroscopy and procedure duration for LBBAP lead implantation. Additionally, this may improve the safety and success of the procedure.

## **Monitoring (Scheduled Follow-up - Visit 2)**

Total period of 2 week (+/- 1 week) starting after baseline visit, during which the subject will be seen in device clinic for routine follow-up to assess device function and to assess any adverse

IRB NUMBER: 2022-0917 IRB Approved: 04/18/2023

events related to the study. Patients will subsequently be followed in the device clinic as per standard of care.

## **Study Exit (Visit 3)**

Once the 3-month follow-up is completed, the subject is considered exited from the study, unless there is unresolved system related AEs with further actions or treatments planned.

#### 4.6 Primary Endpoints

The primary endpoints will be

- Success rate of LBBAP utilizing intraprocedural transthoracic echocardiogram
- Reduction in fluoroscopy/procedure duration for LBBAP lead implantation compared to historic data from prior Geisinger studies utilizing LBBAP
- Identification of work-flow and echocardiographic windows to facilitate LBBAP

# 4.7 Secondary Endpoints

The secondary outcomes will be as follows:

#### 4.8 Statistics

Summary tables of descriptive statistics will be provided for all variables. Continuous variables will be summarized using means and standard deviations or median and interquartile ranges (IQR), depending on distributional assumptions. Categorical variables will be summarized using percentage and frequency counts. The descriptive statistics will be reported for Baseline and follow-up (adverse events only will be collected).

Analysis of the above endpoints will be accomplished using the Chi-square or Fisher's exact tests, and T-tests or non-parametric test (Median test, Wilcoxon rank sum test, etc.), as appropriate.

This study is information gathering and designing workflow. Therefore, any results of statistical tests performed are not conclusive but used to design a larger prospective study.

IRB NUMBER: 2022-0917 IRB Approved: 04/12/2023

## 4.9 Data Management

### 4.9.1 Data Collection and Storage

Data will be collected by research team members, and the resulting analytic file will be stored in a password-protected database on Geisinger's secure network. Only research team members can access the data file. The research team members will review the charts and gather all the needed information. The research team plans to perform manual chart reviews to access any required data elements

The following data, including relevant dates, will be collected:

- Medical record number
- Date of birth/date of death
- Information relevant to all encounters, admissions/discharges, clinical procedures, medications administered, problem list entries, and lab values
- Baseline demographic variables of patients (age, sex, ethnicity, tobacco use, comorbidities)
- Clinical outcomes and procedural related complications

All identifiable date will be stored on a secure server in password protected files. Any hard copy data will be secured in a locked (area/suite/drawer/cabinet), if applicable. Only aggregate data (i.e., no PHI) will be shared with the Sponsor.

#### 4.9.2 Records Retention

Records of data generated during the study shall be retained for at least 6 years and could be used for future research studies submitted and approved by the IRB.

#### 5 SAFETY MONITORING

Echocardiogram is routinely used in clinical practice and is associated with minimal adverse events related to ultrasound gel use on the skin. Rare skin irritation or erythema may be noted. No significant adverse events are anticipated as several thousand ultrasound-based procedures are performed each year in the Geisinger Health System.

IRB NUMBER: 2022-0917 IRB Approved: 04/18/2023

Lastly, we expect patient condition to vary over time. Changes in the patient medical condition in the context of this study is not an adverse event unless directly related to the use of the intraprocedural echocardiogram.

## 5.1 Adverse Event Reporting

Patients will be asked about adverse events related to the use of the echocardiography. These data will not be monitored in real time and patients will be educated on the need to contact their physician directly should they have any medical concern.

Only echocardiogram related adverse event will be collected and reported and then assessed if it is procedure related.

## 5.2 Other Reportable Information.

Geisinger will notify Medtronic and regulatory authorities as applicable for the following incidents immediately upon learning of them:

- An adverse event that led to death.
- An adverse event that led to a serious deterioration in the state of heath that either resulted in:
  - o Life-threatening illness or injury
  - Permanent impairment of a body function or permanent damage to a body structure
  - A condition necessitating medical or surgical intervention to prevent permanent impairment of a body function or permanent damage to a body structure.

IRB NUMBER: 2022-0917 IRB Approved: 04/12/2023

#### **6 PROTECTION OF HUMAN SUBJECTS**

#### 6.1 Informed Consent and HIPAA Authorization

This clinical study will comply with HIPAA. Specifically, the electronic database that will be utilized for the collection of the clinical data that is mandated by this protocol (including personal identifiable information and protected health information) will be HIPPA compliant.

The informed consent will be approved by the IRB and will include the appropriate language that will obtain research participants' authorization for use/disclosure of the information for research purposes (per 45 CFR 164.512(i)(1)(i) (HIPAA)) including the right of the subjects to revoke their consent/authorization as well as disclose his/her right to access the research information (per 45 CFR 164.508 (b) (5) and 164.528).

The investigator will provide for the protection of the subjects by following all applicable regulations. The informed consent/authorization form will be submitted to the IRB for review and approval.

Before any procedures specified in this protocol are performed, a subject must:

- Be informed of all pertinent aspects of the study and all elements of informed consent.
- Be given time to ask questions and time to consider the decision to participate.
- Voluntarily agree to participate in the study.
- Sign and date an IRB-approved informed consent form.

## 6.2 Protection of Human Subjects Against Risks

All electronic study data will be kept in password-protected computer files, and hard copy data will be stored in a locked environment that is only accessible only to the study team members. Data will be coded by assigning a unique study identification number to subjects' medical record numbers. Analysis will be performed using the coded data. Only aggregate data without personal identifiers will be included when presenting results or submitting manuscripts for publication.

IRB NUMBER: 2022-0917 IRB Approved: 04/18/2023

#### 7 PUBLICATION PLAN

We plan to submit a scientific abstract to upcoming meetings and to publish the data as a manuscript in a peer-reviewed journal.

